9.2 Primary Analysis Subgroup Analyses

We will evaluate the primary effectiveness outcome across multiple subgroups. We identified these subgroups as having potential heterogeneity of treatment effect based on likely differences in symptom reporting or treatment patterns:

- Age
- Sex
- Left ventricular ejection fraction
- Charlson comorbidity index (marker of disease comorbidity)
- Baseline KCCQ-12 score
- Prior heart failure cardiomyopathy diagnosis
- Baseline use of recommended therapies

Each of the continuous covariates will be analyzed by modeling the interaction between the continuous covariate and the randomization allocation (KCCQ assessment) along with stratification at the median value. Binary characteristics (e.g. sex) will also be interacted with the randomization allocation.

We will also evaluate the primary analysis among the subgroup with a history of heart failure/cardiomopathy and a baseline KCCQ-12 score of <100.

Secondary Outcomes

Secondary outcomes will include evaluating the effect of KCCQ assessment on heart failure therapy use and healthcare resource utilization. Details regarding each outcomes are listed above in the “Study Outcomes” section. Each secondary outcome will be evaluated using multivariable regression with adjustment for prespecified patient characteristics: age, left ventricular ejection fraction, baseline therapy/utilization, and Charlson Comorbidity Index. A standard regression model will be selected based on the distribution of the outcome. Therapy use (a binary outcome) will be evaluated using multivariable logistic regression. Therapy doses (ordinal outcome) will be evaluated using an ordinal regression model (including no therapy as the base category). The number of medication changes each visit (a count outcome with a high frequency of no medication changes) will be evaluated using a zero-inflated negative binomial model. Hospitalizations and telephone encounters will also be evaluated using a zero-inflated negative binomial model. Clinic visits (count outcomes without a high frequency of zero events) will be evaluated using a standard negative binomial model. For each model, an indicator variable for allocation to the KCCQ assessment arm will be included. The coefficient on this variable represents the effect of PRO collection. Each model will be adjusted for the baseline rate (e.g. hospitalizations or telephone encounters in the prior year) or baseline treatment (e.g. baseline therapies and doses) to improve model precision. Each of the secondary outcomes will be analyzed for the subgroup with a history of heart failure/cardiomopathy and a baseline KCCQ-12 score of <100. For secondary outcomes of treatment intensity (clinic visits, therapy rates, and testing), we will also evaluate if the association between baseline KCCQ-12 and the secondary outcome is significantly larger in the KCCQ arm than the usual care arm.

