4. STUDY OBJECTIVES

PRIMARY AIM

The primary aim of this study is to estimate the impact on heart failure health status in 1 year among outpatients with heart failure who are randomized to routine KCCQ-12 assessment vs. usual care.

SECONDARY AIMS

The secondary aims of this trial are to compare the following outcomes at 1 year in participants randomized to KCCQ-12 or usual care:

- Rates of guideline-directed therapy use
- Dose of guideline-directed medical therapy
- Advanced heart failure therapy evaluation
- Cardiovascular testing
- Heart failure clinic visits (in-person and televisits)
- Heart failure telephone encounters (other than visits)
- Emergency department visits
- Hospitalizations (heart failure and non-heart failure)

[figure not shown]
Additional aims include comparing the following outcomes between participants randomized to KCCQ-12 or usual care:

- Patient experience
- Clinician perception of patients' heart failure health status

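### The single arm coefficient from the zero-inflated count models equals the ratio of mean counts per randomized patient only if the arm leaves structural zeros unchanged

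*Combined protocol and SAP*

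**What the plan says.** Section 9.2, under Secondary Outcomes, chooses a model by the type of outcome. Medication changes are a count per visit, "The number of medication changes each visit (a count outcome with a high frequency of no medication changes", and get a ZINB. The text continues: "Hospitalizations and telephone encounters will also be evaluated using a zero-inflated negative binomial model". Clinic visits get an ordinary negative binomial model, therapy use a logistic model and doses an ordinal model.

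Two sentences then cover every model: "For each model, an indicator variable for allocation to the KCCQ assessment arm will be included" and "The coefficient on this variable represents the effect of PRO collection". On covariates: "Each model will be adjusted for the baseline rate (e.g. hospitalizations or telephone encounters in the prior year", together with age, ejection fraction and the Charlson index. Treating clinician is not in the list, although section 6.3 stratifies randomization by clinician and section 9.1 gives the KCCQ-12 models a clinician intercept.

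Section 4 gives the purpose: "The secondary aims of this trial are to compare the following outcomes at 1 year in participants randomized to KCCQ-12 or usual care". Hospitalizations and telephone encounters are on that list and in the Clinical Trial Summary; the number of medication changes is on neither. Section 8.4 lists medications but not a count of changes. For definitions, the text says "Details regarding each outcomes are listed above in the" and names a Study Outcomes section, but no section has that title. The Summary places resource use at 12 months, whereas section 8.4 has endpoints assessed from 12 to 18 months.

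**The concern.** A ZINB is a mixture. One component gives the probability of being a structural zero; the other gives a negative binomial count for everyone else. An arm term can enter either component or both, and so can each covariate. The plan does not say which, and it names no effect measure. In the logistic, ordinal and ordinary negative binomial models the arm coefficient is identified, so those are not in question.

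The stated aim compares patients as randomized, so the natural target is the ratio of mean events per randomized patient. If KCCQ-12 assessment changes how many patients never have an event, the planned coefficient can understate a difference in mean use, miss it, or show one where the means are equal. Two analysts following the same text could report different effects on hospitalizations.

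The medication-change count raises a separate question. It is defined per visit, but the plan gives no analysis row, patient-level term, clustered standard error or aggregation over visits.

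**Working it through.** **Inputs.** From the documents: the models, the single arm indicator, at least 1,200 patients and 1:1 allocation (600 per arm). The documents give no event rate, share of zeros, dispersion, visits per patient or intraclass correlation (ICC) for these outcomes, so every such value below is assumed. The plan states no figure on this point to reproduce.

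**Identity.** With structural-zero share π and count mean μ, the mean per patient is (1 − π)μ. The ratio of means is therefore

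ratio = (μ1/μ0) × (1 − π1)/(1 − π0).

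The count coefficient gives μ1/μ0. It equals the full ratio only if π1 = π0.

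**Without covariates** (usual care against KCCQ arm, dispersion 0.5). The true ratio is arithmetic; the last two columns are the values to which maximum likelihood converges.

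| Structural zeros | Count mean | True ratio | Arm in count component only | Count coefficient, arm in both |
|---|---|---|---|---|
| 65%, 75% | 1.2, 1.2 | 0.25/0.35 = 0.714 | 0.796 | 1.000 |
| 65%, 70% | 1.2, 1.2 | 0.30/0.35 = 0.857 | 0.904 | 1.000 |
| 65%, 58% | 1.2, 1.0 | (0.42 × 1.0)/(0.35 × 1.2) = 1.000 | 0.947 | 0.833 |
| 65%, 65% | 1.2, 0.9 | 0.9/1.2 = 0.750 | 0.750 | 0.750 |

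With dispersion 1.0 the count-only column is 0.783, 0.897, 0.954 and 0.750.

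**With a baseline covariate**, as the plan intends. The covariate is standard normal, with log-count slope 0.4 and zero-component logit slope −0.6; zeros and count means averaged over it are as above.

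| Zeros (means as above) | True | Count-only, covariate in both | Count-only, covariate in count | Both, covariate in both | Both, covariate in count | Negative binomial |
|---|---|---|---|---|---|---|
| 65%, 75% | 0.732 | 0.811 | 0.747 | 1.000 | 0.967 | 0.711 |
| 65%, 70% | 0.868 | 0.911 | 0.877 | 1.000 | 0.984 | 0.855 |
| 65%, 58% | 0.984 | 0.939 | 0.975 | 0.833 | 0.834 | 1.001 |
| 65%, 65% | 0.750 | 0.750 | 0.748 | 0.750 | 0.722 | 0.750 |

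With stronger slopes (0.6 and −1.0), the first row has true ratio 0.758. Count-only gives 0.825 or 0.716, arm in both gives 1.000 or 0.916, and negative binomial gives 0.708. Thus the count-only miss can shrink or change direction with the placing of the covariate, while the both-components miss stays large. Log-link Poisson regression recovers the true ratio in each case, because randomization makes the covariate independent of arm.

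**Medication changes, if visits were independent rows.** Simulation without an arm effect: 1,200 patients, 4 visits each, structural zeros 50%, mean 0.8, dispersion 0.3, 2,000 trials, nominal two-sided 5%. At ICC 0.058, 0.136 and 0.220 a visit-row ZINB rejects in 6.9%, 10.4% and 18.4% of trials; an analysis of patient totals rejects in 5.0%, 4.8% and 5.7%. As a cross-check, the design effect 1 + 3 × ICC is 1.174, 1.408 and 1.660. Dividing 1.96 by its square root gives error rates of 7.0%, 9.9% and 12.8%. The top of the simulated range therefore depends on the model fitted as well as on the ICC.

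**Visit-count offset.** If visits rose from 4.0 to 4.4 per patient at an unchanged rate per visit, the per-patient ratio would be 4.4/4.0 = 1.10, while an analysis offset by visits would give 1.00.

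**The case against.** The singular wording points to one arm term, and the count component is where most analysts would put it. Under that model the exponentiated coefficient is the covariate-conditional ratio of overall means, so the plan's sentence can be correct. This stands: the figures of 1.00 and 0.83 need arm terms in both components, which is the less literal reading. What remains is an unstated assumption that the arm does not change structural zeros, and an unstated place for the covariates.

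The target is also a choice, since section 4 asks only for a comparison. That is fair, but the plan names no other target, and the mean per randomized patient fits the aim.

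Ordinary negative binomial regression is not a clean replacement. In the three adjusted rows where zeros differ, and in the stronger-covariate case, the count-only ZINB with the covariate in the count component is nearer the true ratio. That also stands and decides the order of the remedies.

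A reader might infer that the planned test has about half the power of the alternatives. In unadjusted simulations at a true ratio of 0.71 it rejected in 33% of trials, against 61% for a robust negative binomial model. The plan adjusts every model, so those rates do not describe it. Nor does an error rate of 18% for medication changes: the plan never says that visits will be treated as independent.

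**Conclusion.** The concern holds for three outcomes. On the literal reading, the coefficient called the effect is the ratio of mean counts only under equal structural zeros; on the other reading, no single coefficient is. In the assumed unadjusted case the reported ratio is 0.80 or 1.00 where the truth is 0.71. With adjustment the count-only error ranges from small to similar, in either direction, and with equal zeros there is essentially none on that reading. Nothing in the documents shows that the arm will change structural zeros, so a reader should not conclude that these results will be biased; the size in this trial is unknown. The primary KCCQ-12 analysis and the logistic, ordinal and ordinary negative binomial models are untouched.

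For medication changes, the count is defined but the handling of repeated visits is not. False positives of about 7% to 18% apply only to independent visit rows with 4 visits and ICCs of 0.06 to 0.22, all assumed, and no listed secondary endpoint is involved. Leaving out treating clinician is a minor inconsistency with the randomization and the KCCQ-12 models; no size is claimed for it. This should be fixed before analysis, but it does not threaten the trial's main conclusion.

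**What to change.** 1. For hospitalizations and telephone encounters, define the effect as the ratio of mean counts per randomized patient. Estimate it by log-link Poisson regression with robust standard errors, or by a ZINB with arm in both components, reporting a standardized marginal mean ratio with a bootstrap or delta-method interval. State where the covariates enter. Keep negative binomial regression with robust standard errors as a sensitivity analysis, because its adjusted coefficient is only approximate for this target.
2. Use one follow-up window, reconciling the Summary with section 8.4, and state how death and person-time are handled.
3. For medication changes, analyse the per-patient total over that window by the same method. Do not offset by visit count, since "Heart failure clinic visits (in-person and televisits" are themselves a secondary endpoint that the arm may change. If a per-visit rate is wanted, label it so and use patient-clustered standard errors. Call the outcome exploratory unless it is added to the endpoint list, and correct the pointer to the missing section.
4. Add treating clinician to the secondary models, with fixed effects as the fallback if random intercepts fail to converge.

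The cost is SAP wording and a little more analysis work, with no new data. When structural zeros are equal, some power is lost: 53% for robust negative binomial against 56% for the count-only ZINB in the assumed unadjusted case with true ratio 0.75. Without covariates, Poisson regression gives the same ratio of arm means as negative binomial. Clinician terms may cause convergence problems.

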8.3 Other Baseline Clinical Data

Baseline clinical values of the following will be extracted from the EHR using structured data elements:

- Demographic characteristics (age, sex, race, ZIP)
- Vital signs, average over prior 3 months
 - Systolic/diastolic blood pressure over previous 3 months
 - Heart rate over previous 3 months
 - Respiratory rate
 - Oxygen saturation
- Most recent BMI
- Comorbidities using diagnosis coding
 - Diabetes mellitus
 - Hypertension

- Hyperlipidemia
- Chronic kidney disease
- Cerebrovascular disease
- Liver disease
- Atherosclerotic cardiovascular disease
- Peripheral vascular disease
- Chronic lung disease
- Major psychiatric disease
- Cognitive dysfunction
- Smoking status
- Cancer
- Prior procedures
 - Implantable cardiac defibrillator
 - Cardiac resynchronization therapy
 - Valve repair/replacement
 - Coronary artery bypass surgery
 - Percutaneous coronary intervention
 - Right heart catheterization
- Lab Results
 - NT-Brain natriuretic peptide
 - Creatinine
 - Hemoglobin
 - Hemoglobin A1c
 - White blood count
 - Blood urea nitrogen
- Echocardiography results
 - Left ventricular ejection fraction
 - Right ventricular systolic pressure
 - Left ventricular internal diameter during diastole
 - Right ventricular systolic function, qualitative
 - Left atrial volume
 - Average E/e'
 - Mitral regurgitation, qualitative
 - Tricuspid regurgitation, qualitative
 - Tricuspid regurgitation peak velocity
 - Estimated right ventricular systolic pressure
 - Left ventricle posterior wall thickness
 - Left ventricle septal thickness
- Medications (specific drug and dose)
 - Beta-blocker
 - Angiotensin-converting enzyme inhibitor

- Angiotensin receptor blocker
 - Angiotensin-receptor neprilysin inhibitor
 - Sodium-glucose co-transporter 2 inhibitor
 - Mineralocorticoid antagonist
 - Long-acting nitrates
 - Hydralazine
 - Loop diuretics
 - Other diuretics
 - Digoxin
 - Statin
 - Aspirin
 - Other antiarrhythmic agents
 - Other blood pressure medications
 - NSAIDs
 - Bronchodilators
 - Inhaled steroids
 - Oral steroids
- Prior Stanford Cardiology Clinic (specific to the affiliated clinician's clinic)
 - Date of last clinic visit
 - Number of clinic visits since 2018
- Other Healthcare utilization
 - Number of total Stanford clinic visits since 2018 (tele-health and in-person)
 - Prior cardiovascular diagnostic tests
 - Electrocardiogram
 - Echocardiogram
 - Stress test
 - CT Coronary Angiogram
 - Invasive coronary angiography)

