 - Number of health system ED visits since 2018
 - Heart failure related
 - Non-heart failure related
 - Number of health system hospitalizations since 2018
 - Heart failure related
 - Non-heart failure related

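### Section 9.2 adjusts utilization outcomes for prior-year rates, but the 8.3 baseline list omits telephone encounters and gives visits and admissions as totals since 2018; this needlessly costs precision, mainly for telephone encounters

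*Combined protocol and SAP*

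**What the plan says.** Section 9.2, under Secondary Outcomes, adjusts every secondary outcome for "age, left ventricular ejection fraction, baseline therapy/utilization, and Charlson Comorbidity Index". It then defines the baseline utilization term: "Each model will be adjusted for the baseline rate (e.g. hospitalizations or telephone encounters in the prior year". The stated purpose covers therapy as well as utilization: "e.g. baseline therapies and doses) to improve model precision". For two of the count outcomes the model is named: "Hospitalizations and telephone encounters will also be evaluated using a zero-inflated negative binomial model".

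Section 8.3 lists the baseline EHR extraction. Its utilization items are:
- "Number of clinic visits since 2018", for the affiliated clinician's clinic, together with the date of the last visit there
- "Number of total Stanford clinic visits since 2018 (tele-health and in-person"
- "Number of health system ED visits since 2018"
- "Number of health system hospitalizations since 2018"
- prior cardiovascular tests, with no look-back window

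Baseline telephone encounters are not listed. Heart failure telephone encounters are nevertheless a secondary aim in Section 4 and an endpoint in Section 8.4.

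**The concern.** The two sections do not describe the same covariates. Telephone encounters are one of only two examples that 9.2 gives for the adjustment, yet 8.3 does not list them at baseline. If the extraction follows 8.3 literally, the telephone model has no baseline value of its own outcome.

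For the other utilization outcomes, a total counted from a fixed calendar date is not a rate. It depends on how long the patient has been in the health system. Eligibility needs only a heart failure clinic visit (Sections 5.3.1 and 8.1), so newly referred patients can enter. For them, a zero may mean that no record exists at this health system. For an established patient, it means low use. The covariates named in 9.2 treat the two alike. The cost would be a wider confidence interval than the available data allow.

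**Working it through.** **Cross-check of the documents**

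| Outcome | Baseline term in 9.2 | Baseline item in 8.3 |
|---|---|---|
| Telephone encounters | prior year (named) | none |
| Hospitalizations | prior year (named) | total since 2018 |
| ED visits | baseline rate | total since 2018 |
| Clinic visits | baseline rate | total since 2018, plus date of last visit |
| Cardiovascular tests | baseline rate | listed, no window |

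**Can the stated adjustment be made?** Baseline and endpoint utilization both come from EHR structured data (8.3, 8.4), extracted through the STARR registry (10.1), and dates are kept relative to an index date (6.8). Telephone encounters are already pulled as an endpoint. Nothing in the documents rules out a prior-year count.

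**Size.** The documents give no event rate, dispersion or power for any secondary outcome, so there is no plan figure to reproduce. All rates below are assumptions. Each run uses 1,200 patients and a plain negative binomial model of the outcome on arm, with or without log(1 + baseline count). The reduction in standard error (SE) is 1 − SE(with)/SE(without).

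*Run 1: telephone encounters, mean 4 per year, gamma shape 0.8, year-to-year fluctuation, 150 replicates.*

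| New patients | No baseline count | Prior-year count | Count + new-patient indicator |
|---|---|---|---|
| 10% | 0.080 | 0.070 | 0.067 |
| 30% | 0.079 | 0.074 | 0.070 |

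- 10% new: 1 − 0.070/0.080 = 12.5%; with the indicator, 1 − 0.067/0.080 = 16%.
- 30% new: 1 − 0.074/0.079 = 6%; with the indicator, 1 − 0.070/0.079 = 11%.
- For clinic visits, the corresponding gain was only 2-3%.

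*Run 2: no new patients; lognormal yearly frailty with correlation ρ between adjacent years; 150 replicates; three-year total as a stand-in for the since-2018 count.*

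| Outcome (assumed rate, frailty variance) | ρ | No count | Prior year | 3-year total | Reduction, prior year |
|---|---|---|---|---|---|
| Telephone (3/year, 0.8) | 0.5 | 0.0633 | 0.0602 | 0.0613 | 5% |
| | 0.8 | 0.0633 | 0.0540 | 0.0542 | 15% |
| | 0.95 | 0.0632 | 0.0483 | 0.0451 | 24% |
| Hospitalization (0.5/year, 1.0) | 0.5 | 0.1060 | 0.1047 | 0.1050 | 1% |
| | 0.8 | 0.1056 | 0.1012 | 0.1005 | 4% |
| | 0.95 | 0.1054 | 0.0979 | 0.0937 | 7% |

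Using the total in place of the prior-year count does little harm. The worst case was telephone encounters with a five-year total at ρ = 0.8: 0.0560/0.0539 = 1.04, so a 4% larger SE (about 8% in variance). With stable risk (ρ = 0.95) the total did better: 0.0451/0.0483 = 0.93 for telephone encounters.

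*Wider range of assumed rates, 10-30% new patients.* For telephone encounters, the count lowered the SE by about 3-14%, and the indicator by a further 5-11% on top of that; together they gave roughly 11-19% compared with no baseline count. For hospitalizations the indicator added only about 0-2%.

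**The case against.** The strongest reply is that 9.2 already prespecifies the prior-year rate and names telephone encounters, so an analyst who follows 9.2 will pull them whatever 8.3 lists. Nothing says that the 8.3 list is exhaustive. Much of this stands. A reader might infer that the stated adjustment is impossible, but the documents do not support that. They show an omission and an inconsistency between two lists.

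A reader might also infer that every utilization endpoint loses precision because the counts run from 2018. The figures above do not support that: since-2018 and prior-year counts perform about equally, and sometimes the longer total does better. Nor would the arm comparison be biased. Every covariate at issue is measured before randomization, and 9.2 gives precision as the reason for adjusting.

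It is tempting to express the gain as 30-40% more patients. That fits only the 10% case in Run 1: (0.080/0.070)² = 1.31 and (0.080/0.067)² = 1.43. With 30% new patients the same arithmetic gives 1.14 and 1.27. The upper figure of each pair also includes an indicator that 9.2 never planned.

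The simulated model is simpler than the planned one. Section 9.2 specifies zero inflation for telephone encounters and adjusts for age, ejection fraction and the Charlson index. Other collected utilization could act as a proxy for the missing telephone count. Having no baseline count at all is therefore the least favourable comparator, and the true gain would be smaller where a proxy is used.

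Two things remain: the telephone count is missing from the list meant to supply it, and no planned term distinguishes new patients from low users.

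**Conclusion.** The point holds as an avoidable loss of precision, chiefly for the telephone-encounter endpoint. Relative to no baseline count, adding the count lowers the SE by roughly 3-14%, and adding the count and the new-patient indicator lowers it by roughly 11-19%. These ranges assume 10-30% new patients, assumed event rates and a plain negative binomial model. The 24% in Run 2 needs nearly constant patient risk and no new patients, so it should not be taken as the expected gain. For hospitalizations and clinic visits the gain is a few percent. Aligning the look-back windows mainly makes the two sections consistent and settles the covariate definition before the data are seen; it is not in itself a material gain in precision.

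Severity is minor. Only secondary outcomes are affected, none has a stated power target, and the primary KCCQ-12 analysis is untouched.

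**What to change.** 1. In 8.3, add heart failure telephone encounters in the 365 days before randomization.
2. In 8.3, define the other baseline utilization counts (clinic visits, ED visits, hospitalizations, tests) over the same 365 days, so that the list matches 9.2.
3. In 9.2, add to each utilization model an indicator for patients with no prior heart failure clinic visit. It can be derived from the visit count and last-visit date already collected. Define it as no prior visit at all; a rule of no visit in the past 365 days would group lapsed established patients with new referrals. Because the 8.3 visit items are specific to the affiliated clinician's clinic, say whether a visit to another heart failure clinician counts.

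The cost is one more EHR item, a date filter on the existing query and one more covariate per model. No patient contact is needed.
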